Number of Participants:	
16 participants randomized 1:1 to immediate start or delayed start intervention
 
Stratification will be performed to divide the number of patients with no to mild fatigue (0-3 numeric rating scale) from patients with moderate to severe fatigue (4-10) because it is possible that the intervention effect is variable depending on baseline level of fatigue.

Study Duration:	Each participant's participation will last up to 6 months.
Study Phases:	Screening for eligibility and obtaining consent
Screening	
Study Treatment	
The exercise coaching program will consist of weekly check-ins for 10 weeks with a certified exercise coach with expertise in caring for oncology patients with a goal of increasing activity to 150 minutes of moderate activity per week. This will be accomplished by shaping behavior through personalized recommendations. Women randomized to the immediate start group will start the intervention during the first week of radiation therapy and continue through and post-completion of radiation. Women randomized to the delayed start group will start the intervention at 6-8 weeks post-radiation.

Follow-Up	Steps, active minutes, patient-reported fatigue, bowel/urinary toxicity, QoL, cognitive function, sexual function and satisfaction, and self-efficacy, as well as distance walked during 6MWT.

Efficacy Evaluations:	
Steps, active minutes, and heart rate measured by a Fitbit device
 
PROMIS Short Form v1.0 – Fatigue 13a (FACT-Fatigue)
 
EPIC Prostate Bowel and Bladder assessment (short form)
 
PROMIS-29 Profile v2.1 QoL (physical function, anxiety, depression, sleep disturbance, pain interference/intensity, ability to participate in social roles and activities)
 
PROMIS Short Form v2.0 – Cognitive Function 4a
 
PROMIS Sexual Function and Satisfaction v2.0 Brief Profile (Female)
 
PROMIS Short Form v1.0 – Self-Efficacy for Chronic Conditions – Managing Daily Activities 4a and Managing Symptoms 4a
 
6MWT

Safety Evaluations:	
Patients can communicate any concerns or safety issues during their weekly check-ins with the exercise coach. They will also be provided with information for contacting an on-call doctor as part of usual care to report any concerning symptoms should they occur outside of the standard evaluation schedule.

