5.3 Allocation to Treatment Groups and Blinding/Randomization

Included subjects were randomly assigned in a 1:1 manner, stratified by baseline fatigue level, using computer-generated numbers. The PI and treating MD will be blinded to the randomization scheme; however, the ultimate allocation to the intervention will not be blinded.

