10.2 Measures to Minimize Bias: Randomization / Blinding

Randomization will be utilized to allocate patients between early and delayed intervention arms. This study will be nonblinded to the patient given the nature of the intervention and nonblinded to the physician due to the nature of the clinical relationship, likely leading to a high chance of patient divulging of the participation in the intervention arm if they are randomized to the exercise coaching intervention. Bias with regard to patient factors will be minimized due to the use of randomization. Bias regarding the rate of activity due to Fitbit monitoring will be present in this study but assumed to be equal between the two groups as both usual care and the intervention groups will be given a Fitbit for monitoring and the use of an attention control check-ins in both intervention groups.

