12.2 Analytics

This study will enroll 16 patients. At the Inova Schar Cancer Institute Fairfax location, approximately 24 patients will undergo a course of pelvic radiation per year. Additionally, approximately 24 patients will undergo a course of pelvic radiation per year across Inova Loudoun, Inova Alexandria, and Inova Fair Oaks Hospitals. With the goal of the study to evaluate adherence to and the acceptability and feasibility of the intervention as part of a pilot study, the sample size was determined with the goal of completing accrual of the study within one year, accruing across all four sites.

Primary Objective Analytical Plan

Feasibility of conducting a randomized trial of this nature will be evaluated on the basis of process feasibility and resources and data-management feasibility.

The *process* feasibility will be evaluated on:

- 1) Recruitment acceptability from the provider and patient perspective:
 - a. Provider acceptability of the intervention will be defined as the proportion of patients identified on pre-screening by the PI that the primary clinician agrees of patient suitability for offering enrollment on the trial and proceeding to completion of screening steps if patient is interested in the study. We set an a priori goal of 50% provider acceptability.
 - b. Patient acceptability of the intervention will be defined as the proportion

of patients who agreed to consent and then proceed to completion of screening steps. We set an a priori goal of 50% patient acceptability.

- 2) Appropriateness of the screening criteria:
 - a. Screening criteria appropriateness will be defined as the proportion of patients who are screened who proceeded to allocation of intervention groups. We set an a priori goal of 50% of appropriateness of the screening criteria.
- 3) Adherence to the exercise coaching session intervention:
 - a. Individual adherence to coaching sessions will be defined as complete adherence when engaging in 10 of the 10 planned exercise coaching sessions and high adherence as engaging in at least 7 of the planned 10 exercise coach check-ins. We set an a priori goal of overall 70% participant adherence to the coaching sessions, to be analyzed per cohort (6 of 8 participants in each arm demonstrating high adherence as defined above).
- 4) Adherence to the physical activity monitor usage to track steps and active minutes:

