 - a. Individual adherence to the physical activity monitor will be defined as wearing the activity tracker for at least 8 hours a day for 70% of the days in the study. Heart rate will be used to determine wear-time. We set an a priori goal of overall 70% participant adherence to the physical activity monitor, to be analyzed per cohort (6 of 8 participants in each arm demonstrating adherence as defined above).
- 5) Adherence to recommendation of 150 minutes per week of moderate physical activity:
 - a. Individual adherence to regular physical activity will be defined as meeting the recommendation of 150 minutes of moderate physical activity per week, based on the Physical Activity Guidelines for Americans developed by the U.S. Department of Health and Human Services (HHS). The target for participant adherence is set at an a priori goal of 70%.

The *resource and management* feasibility will be assessed based on the capacity of the exercise coach and research team to perform the required tasks of the protocol:

- 1) Adherence to the timeline of study procedures and human and data management issues that could potentially arise during a full-scale RCT will be tracked. Adherence to the study timeline for completion of required patient surveys and 6MWT as well as appropriate scheduling (patient attendance not required) of the exercise coaching sessions and follow-ups will be a proxy measurement of research resource and human data management acceptability. We set an a priori goal of 80% adherence.

Secondary Objective Analytical Plan

- 1) Changes in patient-reported fatigue, bowel/urinary toxicity, QoL, cognitive function, sexual function and satisfaction, and self-efficacy, as well as distance walked during 6MWT from baseline to pre-specified time points (end of RT, 5-7 weeks post RT, and 16-19 weeks post RT) within and between each group will be compared using two-sample t-test or Wilcoxon Rank Sum test when appropriate. Repeated measure models/linear mixed effect models may also be used to explore the changes in self-reported questionnaires over time among different treatment groups. Data will be analyzed based on the intention-to-treat principle and used to estimate treatment effect size for future trial design.
- 2) Prevalence of fatigue at baseline in the population of endometrial cancer patients receiving pelvic radiation therapy will be reported using data collected in the screening process.

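### The only committed between-arm analysis is an unadjusted test on change scores, which at 8 per arm lets chance baseline differences into the effect estimate and loses precision if the baseline/follow-up correlation is low to moderate

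*Protocol*

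**What the plan says.** Section 12.2, Secondary Objective Analytical Plan, item 1 (repeated in the synopsis) takes changes from baseline to the end of radiotherapy, 5–7 weeks and 16–19 weeks after it. The outcomes are fatigue, bowel/urinary toxicity, quality of life, cognition, sexual function, self-efficacy and 6MWT distance. These changes "within and between each group will be compared using two-sample t-test or Wilcoxon Rank Sum test when appropriate". No covariate is named.

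The next sentence allows repeated-measures or linear mixed models as a further option. They apply to the self-reported questionnaires only, and no model terms are given. The results are to supply an effect size for the design of a later trial.

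On the design, the synopsis has "16 participants randomized 1:1 to immediate start or delayed start intervention". Section 5.3 states: "Included subjects were randomly assigned in a 1:1 manner, stratified by baseline fatigue level, using computer-generated numbers". The strata are a fatigue rating of 0–3 versus 4–10, chosen "because it is possible that the intervention effect is variable depending on baseline level of fatigue". Section 10.2 adds: "Bias with regard to patient factors will be minimized due to the use of randomization".

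Section 9.3.1 collects baseline values of FACIT-F, EPIC, PROMIS-29, cognition, self-efficacy and 6MWT. The sexual function profile is not among them. Table 1 first schedules it at 5–7 weeks after radiotherapy.

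**The concern.** A change score subtracts the whole baseline value. The best linear prediction of follow-up from baseline, with equal SDs at the two visits, subtracts only the fraction ρ, where ρ is the baseline/follow-up correlation. When ρ is below 1 the change score therefore over-corrects. If one arm happens to start higher, regression to the mean moves its change downward, and the arm contrast inherits that movement.

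In a large trial this hardly matters. With 8 per arm, randomisation removes baseline differences on average but not in the one trial that is run, so the statement in section 10.2 gives limited protection.

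What is at stake is the stated purpose of this aim. The pilot tests no hypothesis, so the product of the secondary analysis is an effect estimate and an SD for the next protocol. A noisier estimate, tied to whatever imbalance occurred, serves that purpose less well than one obtainable from data already being collected.

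**Working it through.** **Inputs from the protocol.** N = 16, allocated 1:1. The adherence goal confirms 8 per arm ("6 of 8 participants in each arm demonstrating high adherence as defined above"). The protocol states no SD, correlation, alpha or power, and "the sample size was determined with the goal of completing accrual of the study within one year", so there is no precision figure of its own to reproduce.

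**Assumptions.** Outcome SD = 1 at both visits; ρ from 0.3 to 0.9; two-sided 95% intervals; normal data. In the simulations, allocation is permuted within two fatigue strata, and the stratifying rating correlates 0, 0.6 or 0.8 with the outcome's baseline.

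**Step 1: chance imbalance.** The arm difference in baseline means has SD √(2/8) = 0.5 outcome SD. For an outcome unrelated to the stratum, P(|difference| > 0.5 SD) = 2 × [1 − Φ(1)] = 0.317, about 32%. Stratified allocation lowers this to about 21–27% for outcomes correlated 0.6–0.8 with the fatigue rating.

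**Step 2: what the imbalance does.** The change-score contrast carries −(1 − ρ) times the imbalance. For a 0.5 SD imbalance the size of the shift is:
- ρ = 0.3: 0.7 × 0.5 = 0.35 SD
- ρ = 0.5: 0.5 × 0.5 = 0.25 SD
- ρ = 0.7: 0.3 × 0.5 = 0.15 SD
- ρ = 0.85: 0.15 × 0.5 = 0.075 SD

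**Step 3: variance by formula.**
- Change score: 2 × 2(1 − ρ)/8
- ANCOVA on baseline: [2(1 − ρ²)/8] × 13/12, where 13/12 is the small-sample cost of one covariate, (N − 3)/(N − 4)

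At ρ = 0.5 these are 0.250 (SE 0.500) and 0.1875 × 13/12 = 0.203 (SE 0.451), a ratio of 0.81. The 95% interval is about 9% narrower (width ratio 0.908, using 14 and 13 degrees of freedom).

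| ρ | SE, change score | SE, ANCOVA on baseline | Variance ratio, formula | Variance ratio, simulated, baseline only | Variance ratio, simulated, baseline + stratum |
|---|---|---|---|---|---|
| 0.3 | 0.592 | 0.496 | 0.70 | 0.72–0.78 | 0.73–0.81 |
| 0.5 | 0.500 | 0.451 | 0.81 | 0.80–0.87 | 0.81–0.91 |
| 0.7 | 0.387 | 0.372 | 0.92 | 0.92–0.94 | 0.95–0.99 |
| 0.85 | 0.274 | 0.274 | 1.00 | no gain | no gain |

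The simulated ranges run from an outcome unrelated to the stratum (largest gain) to one correlated 0.8 with it (smallest gain), because stratification has then already removed part of the imbalance. At the first end they agree with the formula to within about 0.02.

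**Step 4: break-even.** For baseline alone, (1 + ρ)/2 × 13/12 = 1 gives ρ = 24/13 − 1 = 0.85. With the stratum added, simulation puts the break-even near 0.8. The formula with two covariates (factor 13/11) gives 22/13 − 1 = 0.69. It is too pessimistic here because it treats the stratum as free to fall unevenly between arms, and stratified allocation prevents that.

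**Step 5: what the stratum adds.** Once the outcome's own baseline is in the model, adding the stratum raised the simulated SE by about 0.002 to 0.009 in every setting. At ρ = 0.3 and rating correlation 0.8, the unadjusted interval covered 96.8% instead of 95%, and the baseline-only model 95.3%. The stratum term therefore matches the analysis to the randomisation but brings no precision in these settings.

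**The case against.** **The baseline is not ignored.** A reader might infer that the stated test disregards baseline values. It does not: it subtracts them in full, and the fault is over-correction.

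**The estimate is not biased.** A reader might also infer bias. Over repeated randomisations the change-score contrast is unbiased. The shift in step 2 is conditional on the imbalance that happens to occur.

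**The precision loss is not certain.** It depends on a correlation that the protocol does not give. If ρ is about 0.85 or more, ANCOVA gains nothing, and it loses slightly above that.

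**Stratified randomisation does not by itself show that omitting the stratum costs precision.** In the settings tested, the stratum added none beyond the outcome's own baseline. The reason given for stratifying is a possible difference in effect by baseline fatigue. That belongs to the planned moderator analysis, and a main-effect stratum term would not address it.

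**Detail may sit elsewhere.** Model terms are often left to an SAP, which is not shown, and the plan does mention mixed models. This does not remove the point. The t-test or Wilcoxon test is what the protocol says will be done. The mixed models are optional, name no adjustment and omit the 6MWT.

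**The consequence is modest.** This is a secondary aim of a feasibility pilot sized by accrual. With 14 degrees of freedom, the 95% interval for any SD runs from 0.73 to 1.58 times the estimate. That is wider than the gap between the SD of change and the residual SD at ρ = 0.5 (1.00 against √0.75 = 0.87). This stands and limits the weight of the point. So does the remark that the Wilcoxon test is the plan's only stated protection against non-normality, which is a reason to retain it.

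**Conclusion.** The point holds as one of precision and conditional imbalance. The protocol commits its between-arm comparison to unadjusted change scores, although baseline adjustment is available for every listed outcome except sexual function.

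At assumed correlations of 0.3 to 0.7, baseline ANCOVA leaves about 0.72 to 0.94 of the change-score variance. It also removes a shift that would be 0.25 SD for a 0.5 SD imbalance at ρ = 0.5. Imbalances above that size occur in about 32% of such trials for outcomes unrelated to the fatigue stratum, and in 21–27% for outcomes correlated 0.6–0.8 with it.

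These figures rest on equal SDs at both visits, normal data, balanced allocation within strata, and correlations that are assumed because the protocol gives none. The feasibility conclusions are unaffected. The change is worth making because it costs almost nothing and improves the estimates that this aim exists to provide.

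**What to change.** In section 12.2, secondary item 1, and in the synopsis:

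- For fatigue, EPIC bowel/urinary, PROMIS-29, cognition, self-efficacy and 6MWT, take the main between-arm estimate at each visit from a linear model of the follow-up score on arm and the baseline value of the same score. The randomisation fatigue stratum may be added to match the design.
- Report the adjusted difference, its 95% confidence interval and the residual SD.
- Keep the unadjusted comparison of changes (t-test or Wilcoxon) as a sensitivity analysis.
- For sexual function, compare follow-up scores between arms and drop the reference to change from baseline, since no baseline is scheduled.

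This is a wording change with no new data collection. It uses one degree of freedom, or two with the stratum. The downside is a slight loss of precision if the correlation exceeds about 0.85 with baseline alone, or about 0.8 with the stratum as well.

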This study will explore the feasibility of conducting a randomized trial of a personalized exercise coaching program to encourage physical activity for women undergoing adjuvant pelvic intensity-modulated radiation therapy treatment for endometrial cancer to guide the design of future studies to test the hypothesis that a relationship with an exercise coach will increase adherence to exercise. Such a follow-up study will be suited to investigate the effect of exercise to treat or mitigate fatigue, to identify successful strategies for improving adherence to exercise, and to understand which population of patients may benefit most from a targeted program to increase motivation and overcome barriers to exercise.

In this pilot study, a total of 16 women treated with total or modified radical hysterectomy and surgical staging for Stage I-IVA endometrial cancer who are planned to complete pelvic external beam radiation therapy as part of their adjuvant treatment will be included. The intervention is an exercise coaching program which will consist of weekly check-ins for 10 weeks with a certified exercise coach with expertise in caring for oncology patients. The purpose of each check-in is to address readiness for exercise, identify barriers, and develop an individualized plan for exercise for the week with a goal of increasing activity to 150 minutes of moderate activity per week using any form of activity that is enjoyable and accessible to the patient. This will be accomplished by shaping behavior through personalized recommendations. Patients will be randomized to

either an immediate- or delayed-start of their exercise coaching program. Women randomized to the immediate-start group will start the intervention during the first week of radiation therapy and continue through and post-completion of radiation. Women randomized to the delayed-start group will start the intervention at 6-8 weeks post-radiation, a more typical period in survivorship where exercise counseling may begin. Participants will be asked to wear an activity monitor to track steps and moderate activity minutes and to complete assessments of patient-reported cancer-related fatigue, bowel/urinary toxicity, sexual health, and quality of life and participate in a six-minute walk test (6MWT) at predefined time points throughout the study.

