PROMIS Brief Profile Sexual Function and Satisfaction										X		X
Pelvic radiation therapy with IMRT				X	X	X	X	X				
Satisfaction survey												X
Recorded semi-structured exit interview with study PI												X
Early-Intervention Group												
Weekly exercise coach check-ins start x 10 weeks				X (Patients start first check-in during first 5 fractions of RT and continue for a total of 10 weekly sessions. With this schedule, the final session will be post-pelvic RT completion)								
5-10 minute bi-weekly Fitbit check-in call											X (Once every 2 weeks, starting the week after coaching sessions complete for 10 weeks (total 5 calls)).	
Delayed-Intervention Group												
Weekly exercise coach check-ins start x 10 weeks											X (Patients start first check-in after 5-7-week post RT follow-up)	

(Continued) TABLE 1: SCHEDULE OF STUDY PROCEDURES

Study Phase	Screening	Enrollment ¹	RT Simulation	Radiation					Post-Radiation		
Week Number	0		1	(Fraction 1-5)	(Fraction 6-10)	(Fraction 11-15)	(Fraction 16-20)	(Fraction 21-25)	5-7 weeks post RT follow-up ²	6-8 weeks post RT	16-19 weeks post RT follow-up ³
											up, starting 6-8 weeks post RT, and continue for a total of 10 sessions)
5-10 minute bi-weekly Fitbit check-in call				X (Once every 2 weeks starting the first week of RT for a total of 10 weeks (total 5 calls)							

¹Enrollment would occur any time within 7days (before or after) simulation, prior to the start of radiation.

²5-7 week post RT follow-up intended to be soon after completion of intervention in the early-intervention group and before intervention in the delayed-intervention group for purposes of assessment.

³16-19 week post RT follow-up intended to be soon after completion of intervention in the delayed-intervention group for purposes of assessment collection.

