9.3.7 Weekly Exercise coach check-ins x 10 weeks

- Early intervention cohort: Check-in #1 (60 minutes) to occur during the first week of RT (Fx 1-5). Check-in #2-10 (30 minutes) will continue weekly starting Fx 6-10, and continue through the completion of RT and post-RT for a total of 10 sessions.
- Delayed intervention cohort: Check-in #1 (60 minutes) to occur after the 5-7 week follow-up starting 6-8 weeks after pelvic-RT. Check-in #2-10 (30 minutes) will continue weekly a total of 10 sessions.

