9.3.8 Bi-weekly active attention control check-ins x 10 weeks

- Early intervention cohort: Check-ins, once every 2 weeks, with an approximately 5-minute telephone call by a research coordinator to start the week following completion of their exercise intervention (approximately 5 weeks after pelvic RT) for a total of 5 calls.
- Delayed intervention cohort: Check-ins, once every 2 weeks, with an approximately 5-minute telephone call by a research coordinator starting during the first week of RT (Fx 1-5) and continue for 10 weeks for a total of 5 calls.
- The research coordinator will inquire about their use of the Fitbit device, such as if they are wearing it regularly, any technical issues, and if they are syncing their data without discussing physical activity.

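### Section 12.2 takes the treatment effect size from all three visits alike, but by 16-19 weeks both arms have been coached and the contrast is early versus late coaching

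*Protocol*

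**What the plan says.** Secondary objective 1 (Synopsis, Sections 2.1 and 12.1) presents the difference between the immediate and delayed groups at end of RT, 5-7 weeks and 16-19 weeks post RT as initial evidence on the efficacy of the coaching program, meant to guide planning of the follow-up study. Section 12.2, secondary item 1, compares change from baseline to each of these visits within and between groups, allows mixed models as an option, and closes: "Data will be analyzed based on the intention-to-treat principle and used to estimate treatment effect size for future trial design". The synopsis repeats this. Neither place singles out a visit or gives the last one a different meaning.

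The schedule does distinguish them. Under Section 9.3.7 the immediate arm begins coaching in the first week of RT. For the other arm it says: "Delayed intervention cohort: Check-in #1 (60 minutes) to occur after the 5-7 week follow-up starting 6-8 weeks after pelvic-RT". Section 9.3.8 puts the end of the immediate arm's coaching at about 5 weeks after RT. Table 1, footnote 2, places the 5-7 week visit "before intervention in the delayed-intervention group for purposes of assessment", and footnote 3 places the 16-19 week visit shortly after the delayed arm finishes.

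On the purpose of the next trial, the Abstract says: "Such a follow-up study will be suited to investigate the effect of exercise to treat or mitigate fatigue". Section 10.2 describes the comparator as usual care: "both usual care and the intervention groups will be given a Fitbit for monitoring".

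**The concern.** An effect size for planning has to estimate the contrast that the next trial will test. For the effect of coaching, that contrast is coached against not coached, and the design provides it only until the delayed arm starts. After that the randomised comparison is still valid, but it answers another question: whether coaching during RT leaves women better off at 16-19 weeks than coaching after RT.

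Two things are at stake. First, the 16-19 week difference can be near zero or reversed even though coaching works, and any average over the three visits is pulled the same way, so the follow-up trial could be oversized or abandoned. Second, because 12.2 names no visit, the one that supplies the effect size can be chosen after the data are seen.

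**Working it through.** There is no powered figure to reproduce: 12.2 sets the sample size by what can be accrued in one year. The check is exposure arithmetic from the schedule, followed by illustrations on stated assumptions.

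**Inputs.** RT is 25 fractions over 5 weeks (Table 1). Coaching is 10 weekly sessions. The immediate arm starts in RT week 1; the delayed arm starts in post-RT week s = 6, 7 or 8, after the 5-7 week visit (9.3.7). The last visit is in week v = 16 to 19. Synopsis, number of participants: "16 participants randomized 1:1 to immediate start or delayed start intervention", so 8 per arm.

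**Sessions received by the end of the visit week.**
- Immediate arm: session k falls in RT week k, so 5 by end of RT. Session 10 falls in post-RT week 10 - 5 = 5, which agrees with 9.3.8.
- Delayed arm: none up to and including the 5-7 week visit. Session 10 falls in week s + 9 = 15, 16 or 17. At the last visit the count is min(10, v - s + 1). This is 10 in 11 of the 12 combinations of s and v, and 9 at s = 8, v = 16. Counting only weeks before the visit week, the minimum is 8.

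| Visit | Immediate | Delayed | What the contrast measures |
|---|---|---|---|
| End of RT | 5 | 0 | Partial coaching v none |
| 5-7 weeks | 10 | 0 | Full coaching v none |
| 16-19 weeks | 10 | 9-10 | Early v late coaching |

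At the last visit the immediate arm is 16 - 5 = 11 to 19 - 5 = 14 weeks past its final session, while the delayed arm has just finished.

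**Expected contrast at 16-19 weeks.** Let d be the gain from immediate coaching, r the fraction of it still present at 16-19 weeks, and g x d the gain from delayed coaching. All three are assumptions; the protocol gives none. The contrast is (r - g)d.
- With g = 1: 0 at r = 1, -0.25d at r = 0.75, -0.5d at r = 0.5.
- With r and g both between 0.5 and 1: from -0.5d to +0.5d.
- It equals d only if r - g = 1, that is, full retention and a delayed program with no effect.

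**Effect on planning (illustrative).** n per arm = 2(1.96 + 0.84)²/d², two-sided 5%, 80% power. Assume the full d at end of RT and at 5-7 weeks. The average over three visits is 2d/3 if nothing remains at 16-19 weeks, and 2.5d/3 if half the difference remains.

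| Assumed d | From 5-7 weeks | Average, 16-19 week contrast 0 | Average, half remaining | 16-19 weeks alone, half remaining |
|---|---|---|---|---|
| 0.3 | 175 | 393 | 252 | 698 |
| 0.5 | 63 | 142 | 91 | 252 |
| 0.8 | 25 | 56 | 36 | 99 |

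**Precision at 8 per arm.** SE of the change contrast = sqrt(2(1 - rho)) x sqrt(2/8) SD, where rho is the assumed correlation of baseline with follow-up. At rho 0.3, 0.5 and 0.7 this is 0.59, 0.50 and 0.39 SD. Multiplied by t(14) = 2.145, the 95% half-width is 1.27, 1.07 and 0.83 SD.

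ANCOVA on the follow-up score multiplies the SD by sqrt((1 + rho)/2) = 0.81, 0.87 and 0.92, before paying for lost degrees of freedom and chance baseline imbalance. Simulating 8 v 8 with baseline and stratum as covariates (12 df, about 6,000 runs per setting) gives mean CI-width ratios of 0.85, 0.92 and 0.97-0.98.

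**The case against.** The strongest reply is that the protocol never calls the 16-19 week contrast coaching versus no coaching. It describes an immediate-versus-delayed design throughout, lists results visit by visit without pooling them, and explains each visit's role in the Table 1 footnotes. Naming the visit that supplies an exploratory effect size could then be left to the SAP. Nor is the follow-up comparator fixed: the Abstract first mentions a hypothesis about adherence, usual care is a single phrase in 10.2, and the delayed arm receives attention-control calls. End of RT could also be defended as the main visit, since the trial is about fatigue during RT. Finally, with half-widths of 0.83 to 1.27 SD, no visit gives a reliable planning figure.

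Part of this stands. The randomised comparison at 16-19 weeks is valid for timing, and it would be the relevant one if the next trial were to compare early with late coaching. The uncoached comparator is usual care plus attention calls. The sizes above rest on assumed d, r and g. The low precision and the feasibility aim limit the severity.

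The SAP argument does not carry. The objective itself counts all three visits as efficacy of the program, and 12.2 puts them to one use. An SAP that followed this would carry a timing contrast into the effect size, and one that did not would depart from the stated objective. The footnotes show that the authors knew what each visit was for; 12.2 does not carry that over. As for end of RT, only half the sessions have been given by then, while footnote 2 describes the 5-7 week visit as the one after immediate coaching and before delayed coaching.

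**Conclusion.** The concern holds. The exposure pattern of 5 v 0, 10 v 0 and 10 v 9-10 sessions follows from the schedule and needs only that sessions run weekly as planned. The 16-19 week contrast therefore cannot supply a coaching-versus-no-coaching effect size. If both arms gain equally, its expected value is zero with full retention and -0.5d with half retention. At an assumed d of 0.5, averaging a zero contrast with two full ones would raise the follow-up trial from 63 to 142 per arm. These sizes are illustrative, because the protocol gives no effect size, SD or retention figure.

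This should be corrected but does not threaten the trial. It touches a secondary, exploratory aim in a 16-patient pilot, although sizing the next trial is that aim's stated purpose.

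**What to change.** In 12.2 and its copy in the synopsis:

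- State that the coaching effect size is the between-arm difference at 5-7 weeks post RT, with a 95% CI.
- Treat end of RT as supportive, since coaching is only half delivered.
- Report 16-19 weeks as immediate-versus-delayed timing or durability, and as within-arm change, for which the visit is needed in the delayed arm. If a mixed model is used, keep this visit out of any pooled group effect.
- Optionally, for precision only (change scores are unbiased under randomisation), estimate the 5-7 week difference by ANCOVA on the follow-up score, with its baseline value and the fatigue stratum as covariates. The stratum is already part of the allocation in 5.3: "Included subjects were randomly assigned in a 1:1 manner, stratified by baseline fatigue level, using computer-generated numbers".
- Sexual function is first collected at 5-7 weeks (9.3.5) and is not among the baseline assessments in 9.3.1, so change from baseline cannot be computed. Compare its follow-up scores, adjusted for stratum only.

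The cost is wording in two places, with no new visits or data. ANCOVA, if used, takes two degrees of freedom, or one for sexual function.
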